Options that have been recommended by WHO to ensure earlier diagnosis and reduce mortality include strategic placement of rapid molecular TB diagnostics such as Xpert²¹ or Ultra²² within HIV care settings (which could enable availability of results within 24 hours), and uptake of the lateral flow urine lipoarabinomannan assay (LF-LAM)²³ strip-test – the Alere Determine™ TB LAM Ag (AlereLAM) for seriously ill PLHIV. However, despite AlereLAM being a cheap and fast test, only 9 of the 30 high TB and HIV burden countries have a national policy and algorithm indicating the routine use of urine LF-LAM (with various levels of implementation).² A recent study showed that urine-based TB screening of PLHIV admitted to hospital might reduce 56-day mortality in those with low CD4 counts, severe anaemia or clinically suspected tuberculosis.²⁴ A recently published meta-analysis showed that, as a screening test among PLHIV, AlereLAM has limited sensitivity of 45% (95% CI: 29-63) and specificity of 92% (80-97) against a composite microbiological reference standard.²⁵ However, screening with AlereLAM improves the likelihood of being diagnosed with TB during admission. The WHO recently expanded the recommendations for the use of AlereLAM to include adults, adolescents and children living with HIV with signs and symptoms of TB (inpatient and outpatient setting) or irrespective of signs and symptoms of TB with CD4 cell count under 200 cells/mm³ in inpatient settings irrespective of the CD4 cell count in outpatient settings.²⁶ The unavailability of CD4 counts upon admission or the assessment of the criteria for severely-ill or advanced HIV disease might delay quick testing of PLHIV in whom AlereLAM is recommended. In addition, LAM tests do not provide any information on potential resistance to anti TB drugs, which might hinder its implementation in high TB drug resistance settings.

The limitations of existing sputum-based tests for *M. tuberculosis* (*Mtb*) diagnosis create imperatives to explore the usefulness of easy to collect, non-respiratory specimens which could improve performance of all tests, while supporting treatment guidance and monitoring. In fact, the WHO has specified the need for rapid non-sputum based TB diagnostics among their high priority target product profiles for new TB diagnostics.²⁷

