8.3 Exploratory endpoints

- Diagnostic performance of a molecular TB diagnostic assay (Xpert Ultra and/or LumiraDx) on tongue swabs, and FujiLAM on urine against a microbiological reference standard (as defined in intervention arm) or against a composite reference standard that includes bacteriologically confirmation or/and clinical evidence resulting in therapy initiation. This endpoint will only be studied in participants of the intervention arm
- Diagnostic accuracy of CRP in blood in order to evaluate compared to TB symptom's screening in those with microbiologically confirmed TB.
- Comparison of primary and secondary endpoints of the intervention arm with the local standard of care at the sites before the study initiation (a retrospective data collection from consecutive HIV-positive patients admitted at participating hospitals).

This project is part of the EDCTP2 programme supported by the European Union

9. Trial Design and study arms

This is a multicentre, parallel, individually randomized controlled diagnostic trial in consecutively enrolled HIV positive adults to evaluate the impact of the extended use of Xpert Ultra (3 specimens) for TB diagnosis, using sputum, stool and urine, AlereLAM among consecutive PLHIV admitted to hospitals in 4 sites of 2 high burden African countries (Tanzania and Mozambique). Thus, the **intervention arm** for this trial will include TB testing performed irrespective of the presence of TB symptoms. Testing will be done on expectorated sputum, stool and urine with Ultra and urine with AlereLAM.

To fulfil exploratory objectives, we will also collect 2x tongue swabs for molecular TB diagnostic assay (Xpert Ultra and/or LumiraDx) testing, blood for CRP, and urine samples which will be stored for retrospective FujiLAM testing and analysis.

The **control arm** for this trial consist of patients managed according current WHO testing recommendations (as of Q1 2020) for HIV-positive inpatients. TB testing will be done as follows:

- a) ***Sputum Ultra*** whenever the patient has cough, fever, weight loss or night sweats and/or Ultra performed on any tissue (including lymph nodes) in patients with clinical suspicion of extrapulmonary TB.
and/or
- b) ***Urine Alere TB-LAM***, if patients have signs and symptoms of TB (pulmonary and/or extrapulmonary), or with advanced HIV disease or who are seriously ill or else irrespective of signs and symptoms of TB and with a CD4 cell count of less than 200 cells/mm³.

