10.10 Follow up procedures (table 2)

Hospitalization stay (daily)

During hospitalization (daily) and at discharge, study team will verify and record whether a TB diagnosis has been made and/or anti TB treatment started. The study team will be working jointly with the routine health care staff so clinical decisions are made jointly. Study team will also record any ad-hoc TB investigation (additional Ultra, LAM testing, X-ray, etc) and their result. HIV care will follow national guidelines. .

Scheduled visits

After enrolment, there are two scheduled visits that need to take place unless the patient remains hospitalized (week 4 and week 8). These visits can occur either in the outpatient clinic, as home visits or by call or video-call depending on the patient and team preferences and COVID-19 epidemiologic situation. However, outpatient visits are recommended. A member of the study team will verify whether a TB diagnosis has been made on the relevant medical records (hospital or NTP office) and/or anti TB treatment started after discharge. Study staff will also record any ad-hoc TB investigation that was initiated by the care provider for clinical reasons (additional Ultra, LAM testing, X ray, etcetera) and their result (both by checking patient records and by asking the patient). HIV care will follow national guidelines. Vital status will also be recorded at these two visits. These visits will have a window period of -/+ 3 days (at week 4) and -3/+7 days at week 8.

In case a discharged participant does not attend the week 4 or week 8 visit, three phone call attempts will be made and, if unsuccessful, at least one home visit will be performed in order to collect relevant data to that visit. These attempts should be recorded in a patient tracking log. Week 4 visit should be sought until week 8 window visit opens, although will be considered a protocol deviation if done outside the week 4 window visit.

This project is part of the EDCTP2 programme supported by the European Union

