13.1 Sample Size calculations

Recent studies using Alere LAM and sputum Xpert to screen unselected admitted HIV positive patients in Southern Africa^{24,29,31} show that around 17% of these patients are laboratory confirmed for tuberculosis. The added yield of using Xpert Ultra instead of Xpert would involve an 11-17%⁴³⁻⁴⁵ relative increase in bacteriological confirmation. Thus, universal AlereLAM testing and sputum Ultra would likely confirm around 20% of unselected admitted HIV participants in our study. We estimate that the bacteriological confirmation in our control arm would be slightly lower than 20%, around 19%, given that we will not use a universal screening strategy but the WHO recommendations (sputum Ultra if TB compatible symptoms and AlereLAM testing if TB compatible symptoms or in those with advanced HIV disease, or seriously ill, or with a CD4 cell count of less than 200 cells/mm³). Based on existing literature, we estimated that up to 10% of participants in our control arm would not receive either Xpert Ultra or LAM testing.

We estimated that the intervention arm would yield around 26% of bacteriologically confirmed cases by universal testing (irrespective of symptoms) with AlereLAM and Xpert Ultra on sputum, urine, and stool. As mentioned before, universal AlereLAM and sputum Xpert Ultra would yield around 20% of bacteriological confirmation. Studies show that Xpert urine could increase bacteriological confirmation by 4%. Although there is limited evidence on the potential benefits of stool Xpert Ultra in adults, there are promising results observed in children (who, as HIV positive patients, often have extrapulmonary TB). Thus, we assume that adding stool Xpert could increase our bacteriological confirmation about 1%. If we apply a similar gain (observed in sputum) in urine and stool by substituting Xpert by Ultra, the combined added yield would be of around 6%. Thus, we expect to have a 26% bacteriological confirmation in our intervention arm by using universal LAM testing and Xpert Ultra on sputum, stool and urine. This would translate into a 7% difference (19-26%) between our control and intervention arm.

The estimation of the bacteriologically confirmed cases in both the control and intervention arm could have the following limitations:

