13.2.2 Statistical methods

Variables will be summarized using descriptive statistical methods. Continuous data will be described using the mean and standard deviation statistics when these values follow the normal distribution. Otherwise we will use the median and interquartile range when we will not assume this distribution. Categorical values will be summarized using frequency and/or percentages.

For categorical comparisons we will use a Chi-square test or Fisher exact test according to the

This project is part of the EDCTP2 programme supported by the European Union

data characteristics. Likewise, the continuous comparisons will be tested by Student t-test, Anova test or Kruskal Wallis test.

When necessary, we will transform the continuous data, especially laboratory data, in non-linear scale. For these cases we will describe these data with geometric mean. Heterogeneity between sites will be analyzed.

Assessment of loss to follow-up as random across arms

We will analyze the baseline characteristics between lost and non-lost follow up patients and across arms to ensure that loss to follow up occurs randomly. If we find any significant attribute we will adjust the analysis by this/these factors.

Time-to-event data

Time-to-event data (such as time to mortality, time to TB diagnosis or time to treatment initiation (among lab confirmed or all TB)) will be presented using Kaplan-Meier curves with a log rank test (two-sided 0.05 significance level). The analysis of covariates on time-to-event data will be performed using a Hazard Ratios estimated through Cox regression models.

Comparisons between control and intervention arm will be established at prespecified time points (day 7, day 14, day 28 and day 56). Mean time (and SD) to event per study arm will also be estimated.

Significance levels

The significance level for most comparisons is $p=0.05$. For selected secondary endpoints measured at several timepoints and subgroup analysis, the significance level will be $p=0.01$

Study discontinuations & patient disposition

Patient disposition and reasons for premature discontinuations and their frequencies will be tabulated.

Datasets analyzed

Number of patients in each analysis set will be tabulated and listings of any patients excluded from any analysis set will be provided.

Efficacy analysis

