### 3.4 Endpoints

All study endpoints will be compared between control and intervention arm. Also, the final results will be presented disaggregated by sex.

3.4.1 The **primary endpoint** is the proportion of participants diagnosed with microbiologically confirmed TB and started on TB treatment within 72 hours of enrolment\* in whom TB is microbiologically confirmed\*/\*\*

\* The numerator of the primary endpoint includes participants per study arm who are diagnosed with microbiologically confirmed TB and initiated TB treatment within 72 hrs of enrolment. The denominator is the number of enrolled participants in each study arm.

\*\* Participants are defined to have microbiologically confirmed TB if at least one confirmatory TB test (Ultra, AlereLAM) gives a positive result.

**Secondary endpoints** are:

Related to main objective

3.4.2.1 Time-to-TB-treatment-initiation among microbiologically confirmed cases and among all TB cases since enrolment. We will estimate Kaplan Meier curves and hazard ratios at day 7, 14, 28 and 56. Additionally we will compare the time to related estimates (median and IQR) of intervention and control group.

3.4.2.2 Proportion of cases re-admitted to hospital. The numerator will be the number of admissions for any reason (not included in the exclusion criteria) after initial discharge and within 8 weeks from enrolment. The denominator will be the number of participants enrolled.

---

3.4.2.3 Proportion of participants who are diagnosed with TB (irrespective of bacteriological confirmation) and have started on TB treatment within 72 hours of enrolment.

3.4.2.4 Proportion of participants who are diagnosed with microbiologically confirmed TB and are started on treatment at 7, 14 days and 8 weeks of enrolment.

3.4.2.5 Time to laboratory confirmed TB diagnosis and any TB diagnosis since enrolment.

3.4.2.6 Proportion of microbiologically confirmed TB participants started on treatment without Rif resistance information (only AlereLAM positive)).

Related to secondary objectives.

3.4.2.7 Eight-week all-cause mortality. The numerator will be the number of deaths during eight weeks after enrolment, the denominator the number of participants enrolled.

3.4.2.8 In hospital and 4-week all-cause mortality among all participants enrolled (assessed as the eight-week all-cause mortality).

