### 8.2 Secondary Efficacy Analyses

All secondary efficacy analyses will be calculated on ITT and Per protocol populations. The Secondary Efficacy Analyses are:

8.2.1 We will compare the proportion of deaths during eight weeks after enrolment between all participants enrolled in two study groups. We will test this differences using the test statistics  $z$  has an asymptotic standard normal distribution. These groups are microbiologically confirmed TB and therapy initiated within 72 hours from admission (numerator/success) and non-lab-confirmed TB or therapy not initiated within 72 hours (denominator/failure). We will compare, using Chi-square test or Fisher Test, these proportion values between intervention and control group.

8.2.2 We will estimate the Kaplan Meier curves to assess time to TB treatment initiation among those with microbiologically confirmed TB and among all TB (also including clinically diagnosed). We will compare both arms using the log rank test. We will use the KM procedure to calculate the survival rate from the survival function. If deemed necessary, to study the effects of some covariates and start of treatment over time we will use the Cox regression.

8.2.3 We will compare the proportion of cases re-admitted to hospital, to test this proportion we calculate the number of admissions after initial discharge and within 8 weeks from enrolment from all participants enrolled. We will compare, using Chi-square test or Fisher Test, these proportion values between intervention and control group.

8.2.4 We will compare the proportion of participants who are diagnosed with TB (irrespective of bacteriological confirmation and are started on TB treatment within 72 hours of enrolment). We will compare, using Chi-square test or Fisher Test, these proportion values between intervention and control group.

8.2.5 We will calculate the proportion of participants who are diagnosed with microbiologically confirmed TB and are started on TB treatment at 7d, 14d, 4 and 8 weeks of enrolment. We will compare, using Chi-square test or Fisher Test, these proportion values between intervention and control group.

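### The log-rank test of time to TB treatment (SAP 8.2.2) is restricted to cases found after randomisation, and the per-protocol set in protocol 13.2.3 is conditioned on part of the primary endpoint; the primary ITT comparison is unaffected

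*SAP*

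**What the plan says.** **Time to treatment.** SAP 3.4.2.1 defines this endpoint "among microbiologically confirmed cases and among all TB cases since enrolment". SAP 8.2.2 analyses "time to TB treatment initiation among those with microbiologically confirmed TB and among all TB", compares the arms by log-rank, and allows Cox regression if needed. Protocol 13.2.2 agrees: time-to-event data, including "time to treatment initiation (among lab confirmed or all TB"), are to be "presented using Kaplan-Meier curves with a log rank test (two-sided 0.05 significance level").

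**Who becomes a case.** The intervention arm has sputum, stool and urine tested in everyone (protocol 10.9.1). Controls are tested only if they meet symptom or severity criteria (10.9.2). For controls, protocol section 9 also lists "Ultra performed on any tissue (including lymph nodes) in patients with clinical suspicion of extrapulmonary TB", which it does not list for the intervention arm. On expected confirmation, protocol 13.1 says: "This would translate into a 7% difference (19-26%) between our control and intervention arm".

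**Related comparisons.**
- SAP 8.2.4 compares any-TB treatment at 72 hours.
- SAP 8.2.5 compares confirmed-and-treated proportions at 7 and 14 days and 4 and 8 weeks, at the 0.01 level set in SAP 6.3.
- Protocol 8.2 adds a right-censored version of that endpoint, censoring at loss to follow-up or death.
- SAP Table 3 has p-value columns for hours to treatment (started by 72 hours) and days to treatment (started later).

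**Per-protocol set.** Protocol 13.2.3 takes participants whose result was available and who started treatment within 72 hours. SAP 6.1.1 instead requires complete samples and results within 72 hours, with no treatment condition. SAP 8.1 and 8.2 report per-protocol results beside ITT. SAP 6.2 compares the two to judge missing intervention- and visit-related values.

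**The concern.** Randomisation makes the enrolled groups comparable, not the subgroups labelled as TB cases afterwards. Broader testing changes who is labelled. If the additional cases are treated more slowly than cases both arms would find, the intervention can look slower although more of its patients are treated early. If many control cases are confirmed late, it can look faster by a margin that depends on who was eventually found. Earlier treatment is the mechanism the trial proposes, so this result will be interpreted.

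The per-protocol problem is related. If everyone in the set was treated within 72 hours, the primary endpoint there is only the confirmed share of treated patients. That share moves with empirical treatment, which is the physician's decision in an unblinded trial. A shift produced by the filter could then be read as an effect of adherence or of missing data.

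**Working it through.** **1. The plan's own figure.** For 19% versus 26%, two-sided 0.05 and 80% power, the pooled normal formula gives 558 per arm. 558 × 1.05 = 586, the stated figure.

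**2. Who enters the case-only test.** 0.19 × 586 ≈ 111 controls and 0.26 × 586 ≈ 152 intervention participants: 264 of 1172 (22.5%), split 42:58.

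**3. Proportion treated by 72 hours.** Assumptions: 19% shared cases, of whom 90% start within 72 hours in both arms; 7% extra intervention cases, of whom 60% start within 72 hours; a fraction f of the matching controls confirmed after 72 hours.

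- Intervention cases: (0.19 × 0.90 + 0.07 × 0.60) / 0.26 = 0.213 / 0.26 = 81.9%.
- Control cases: 0.171 / (0.19 + 0.07f).

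| f | Control cases | Intervention cases | Difference (points) |
|---|---|---|---|
| 0 | 90.0% | 81.9% | −8.1 |
| 25% | 82.4% | 81.9% | −0.5 |
| 50% | 76.0% | 81.9% | +5.9 |

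Among all randomised participants the figures are 17.1% versus 21.3% (+4.2) in every row. Only the case-only contrast changes sign.

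**4. Log-rank simulation.** 586 per arm; exponential treatment times with daily rate −ln(1 − p)/3, where p is the assumed 72-hour proportion; shared intervention cases at 90%; late controls treated uniformly over days 3–56; censoring at day 56; 4,000 trials per cell (Monte Carlo SE at most 0.8 points). Selected case-only results at two-sided 0.05:

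| Extra cases by 72 h | Shared controls by 72 h | f | Result |
|---|---|---|---|
| 60% | 90% | 0 | 63% against |
| 60% | 90% | 10% | 12% against |
| 60% | 90% | 25% | 0.4% against |
| 60% | 90% | 50% | 69% for |
| 60% | 85% | 0 | 14% against |
| 60% | 80% | 0 | 1% against |
| 75% | 90% | 0 | 23% against |
| 90% | 90% | 0 | 2.6% against, 2.4% for (nominal) |
| 90% | 90% | 50% | 98% for |

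The all-randomised test was against the intervention in no more than about 0.1% of trials in any cell. It was for it in 78–86% (f = 0), 55–67% (f = 25%) and 30–41% (f = 50%). With 15% or 25% deaths by week 8, equal in both arms, the first row becomes 63% and 61% against. The all-TB comparison cannot be sized, because the documents give no rates for clinically diagnosed TB.

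**5. Protocol 13.2.3 set, no true effect.** Let 0.19 × 0.90 = 17.1% be confirmed and treated in both arms. The endpoint in the set is 17.1 / (17.1 + unconfirmed treated). With 5% treated empirically it is 17.1 / 22.1 = 77.4%; with 10%, 17.1 / 27.1 = 63.1%. A 5% versus 10% difference in empirical treatment therefore produces a false difference of 14.3 points, its sign set by which arm treats more empirically.

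**6. SAP 6.1.1 set, no true effect.** If participants with the endpoint complete the intervention samples k times as often as others, and the filter is neutral in controls, the intervention proportion is pk / (pk + 1 − p) with p = 0.171. For k = 0.8 this is 0.1368 / 0.9658 = 14.2%; for k = 1.25 it is 0.21375 / 1.04275 = 20.5%. Against 17.1%, the false difference runs from −2.9 to +3.4 points.

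**The case against.** The strongest reply is that the plan already compares treatment start without restricting to cases. For confirmed TB there are the primary endpoint, SAP 8.2.5 and the right-censored version in protocol 8.2. This largely stands. A reader might infer that 8.2.2 is the only planned between-arm comparison of treatment timing; it is only the one named time-to-event test of it. In 12 simulated cells, 8.2.5 at its 0.01 level was never significantly against the intervention, so a reversed 8.2.2 result would sit beside results that do not reverse. For any TB, however, nothing outside cases is compared after 72 hours.

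A reader might also infer from the 63% that the test is biased against the intervention. The documents do not support a direction. Protocol 5.1 says that assessing the criteria "might delay quick testing of PLHIV in whom AlereLAM is recommended", so shared controls may be slower. Protocol 10.10 says "Study staff will also record any ad-hoc TB investigation that was initiated by the care provider for clinical reasons", so late confirmation can occur. Mild departures bring the test near nominal: with extra cases at 60%, shared controls at 85% and 10% late, 1.2% against and 5% for; with extra cases at 75%, shared controls at 90% and 10% late, 2.4% and 3.4%. Distortion the other way remains: extra cases at 60%, shared controls at 85% and 25% late give 42% for.

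The simulation nests control cases within intervention cases. In practice neither set need contain the other, since tissue Ultra is listed only for controls, although SAP 4.4 records Ultra on other specimens without naming an arm. The 7 points are a net difference.

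On the per-protocol set, protocol 13.2 leaves analysis details to the SAP, and SAP 6.1.1 drops the treatment condition. The 14.3 points therefore apply to the protocol wording only.

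**Conclusion.** The point holds for a supporting analysis. The case-only log-rank compares groups formed after randomisation by arm-specific testing, so its result cannot be read as the effect on time to treatment. The distortion has no fixed size or direction: with shared controls at 90% it runs from 63% significantly against, in a corner case, through about nominal, to 69–98% significantly for with half the matching controls confirmed late. All timing rates are assumptions. The Table 3 p-values condition more narrowly still, on having been treated.

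The two per-protocol definitions conflict. One conditions on part of the primary endpoint; the other filters on sample completion, which differs by arm. Neither can show whether missing data matter.

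A reader might extend this to the main result. That does not follow: the primary endpoint's denominator is everyone enrolled, the ITT set is everyone randomised, and SAP 6.3 keeps formal inference for the primary objective. The change should be made, but the trial's main conclusion does not depend on it. Confidence is medium, because the size rests on assumed rates.

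**What to change.** 1. **SAP 8.2.2, 3.4.2.1 and protocol 13.2.2.** Make the between-arm test time from randomisation to treatment start with confirmed TB, and with any TB, among all randomised participants, with death as a competing event. Align the right-censored version in protocol 8.2, which now censors at death. Keep the case-only curves and the Table 3 hours and days rows as description, without between-arm p-values.
2. **Protocol 13.2.3 and SAP 6.1.1.** Use one per-protocol definition, without treatment start as a condition and with controls who met no testing criterion kept in. Label per-protocol results supportive.
3. **SAP 6.2.** Do not use ITT versus per-protocol as evidence on missing data. For endpoint variables use the best/worst-case analysis already planned, and correct its mixed scenario, which assigns both best and worst to the intervention arm, to best in one arm and worst in the other. That analysis covers only main endpoint variables above about 5% missing, so missing samples and visits should be tabulated by arm with the reasons already collected.

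The cost is wording and a little programming on dates already collected; the sample size does not change. The drawback is power: if half the matching controls are confirmed late, the all-randomised test detects the difference in only 30–41% of trials under these assumptions, fewer than the case-only test.

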8.2 Secondary endpoints

- Eight-week all-cause mortality (main secondary endpoint) among all participants enrolled. The numerator will be number of deaths during eight weeks after enrolment, the denominator is the number of participants enrolled. We will compare this indicator between both study arms. In addition, this endpoint will also be calculated considering right censored observation when a participant is lost to follow up during the observation period or a

This project is part of the EDCTP2 programme supported by the European Union

participant experiences a different event that makes further follow up impossible.

- Time to TB treatment initiation among microbiologically confirmed cases and among all TB cases since enrolment. We will estimate Kaplan Meier curves (event= TB treatment initiation among laboratory confirmed TB patients and among all TB cases) and hazard ratios at day 7, 14, 28 and 56. Additionally we will compare the time to related estimates (mean and standard deviation) of intervention and control group.
- Proportion of cases re-admitted to hospital. The numerator will be the number of admissions after initial discharge and within 8 weeks from enrolment. The denominator will be the number of participants enrolled.
- The proportion of participants who are diagnosed with TB (irrespective of bacteriological confirmation) and started TB treatment within 72 hours of enrolment. The numerator is the number of participants diagnosed with TB (with or without bacteriological confirmation) who started treatment within 72 hours of enrolment; the denominator is the number of participants enrolled.
- The proportion of participants who are diagnosed with microbiologically confirmed TB and are started on treatment at 7 days, 14 days, 4 weeks and 8 weeks of enrolment. In addition, this endpoint will also be calculated considering right censored observation when a participant is lost to follow up or dead during the observation period or a participant experiences a different event that makes further follow up impossible.
- Proportion of participants who are able to provide sputum, stool and urine samples for Ultra/AlereLAM testing within 24, 48 and 72 hours of enrolment (the numerator is the number of urine samples or (and) sputum samples provided within 72 hours of admission and the denominator is the number of patients enrolled).

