## 5 Sample Size

We expect the absolute difference in proportions of bacteriological confirmation between the two arms to be 7% (from 19% to 26% from the control to the intervention arm). Sample size was chosen to be sufficient to detect a 36.8% relative increase in the primary outcome in the intervention arm (as compared to the control arm).

Under this premise and the following assumptions:

- Alpha (two sided): 0.05
- Beta (power 80%): 0.2
- Estimated proportions of participants with microbiologically confirmed TB in the control arm 19% and in the intervention arm 26%
- Lost to follow up: 5% of recruited participants.

The study will recruit 586 PLHIV participants per trial arm, then we will include in the analysis 1172 participants in total. This number of participants will come from 4 sites (293 participants per arm at each site).

For this calculation we have used the following formulas based on Normal asymptotic approximation for proportions:

Sample Size formula

$$n_1 = \frac{\left( Z_{1-\alpha/2} \sqrt{(1 + \varphi) \bar{p}_1 (1 - \bar{p}_1)} + Z_{1-\beta} \sqrt{\varphi p_1 (1 - p_1) + p_1 (1 - p_1)} \right)^2}{\varphi |p_1 - \bar{p}_1|^2}$$

Power formula

$$\varphi = \frac{1 - w_1}{w_1}$$

$$\bar{p} = \frac{p_1 + \varphi p_2}{1 + \varphi}$$

$$1 - \beta = \Phi \left( \frac{|p_1 - \bar{p}| \sqrt{\varphi w_1} - Z_{1-\alpha/2} \sqrt{(1 + \varphi) \bar{p} (1 - \bar{p})}}{\sqrt{\varphi p_1 (1 - p_1) + p_2 (1 - p_2)}} \right)$$

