### 6.3 Multiple Testing

We consider unnecessary to apply a general adjustment of significance level by multiple comparisons test. We will use the all the statistical power for inference only in the primary study objective. To evaluate the other study endpoints, we use the p-value threshold at 0.05 to find the differences in our study without the objective to extrapolate the results to the global community. However, we will establish a p-value of 0.01 as a threshold for statistical significance in the comparisons related to a) selected secondary efficacy analyses (section 8.2, analyses 8.2.5, 8.2.6, 8.2.7) and subgroup analysis (see section 9.0)

We will adjust the results by site, demographic variables, and other baseline variables if we will detect differences or if these variables have a confounder characteristics profile. To decide this, we will do a preliminary analysis of these variables between sites.

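### The readmission endpoint is labelled a proportion of cases but counts admissions, so chi-square/Fisher is anti-conservative if anyone is readmitted more than once

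*SAP*

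**What the plan says.** The label describes a share of people. SAP 8.2.3 opens: "We will compare the proportion of cases re-admitted to hospital".

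The numerator is a count of events wherever it is defined:

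- Protocol 8.2 (and the synopsis): "The numerator will be the number of admissions after initial discharge and within 8 weeks from enrolment".
- SAP 3.4.2.2: "The numerator will be the number of admissions for any reason (not included in the exclusion criteria) after initial discharge".
- SAP 8.2.3: "we calculate the number of admissions after initial discharge and within 8 weeks from enrolment from all participants enrolled".

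The denominator is a count of people. SAP 3.4.2.2: "The denominator will be the number of participants enrolled".

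The test is the standard one for two proportions. SAP 8.2.3: "We will compare, using Chi-square test or Fisher Test, these proportion values between intervention and control group". Analysis 8.2.3 is not among those that SAP 6.3 holds to 0.01, so the general rule for the other endpoints applies: "we use the p-value threshold at 0.05 to find the differences in our study".

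Nothing in either document limits the count to the first readmission per person. The derived variables in SAP 7.2 include no yes/no readmission indicator, and the variable tables in SAP 4.4 list no readmission item.

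**The concern.** Chi-square and Fisher tests on a two-by-two table require each person to fall in exactly one cell. With admissions in the numerator, the second cell becomes enrolled minus admissions, which is not the number of people without a readmission. Two things follow once anyone is readmitted more than once:

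- The reported proportion is larger than the share of participants readmitted. If repeats are more common in one arm, a difference appears even where the same share of people is readmitted in both.
- The binomial variance behind the test is too small, so the p-value is too small.

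Label and numerator also point to two different analyses. One programmer could follow the label and another the numerator, and both could claim to have followed the SAP. The ambiguity carries into the per-protocol version of the analysis and the analysis of secondary endpoints by sex.

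**Working it through.** **The plan's own figures.** The documents give no readmission rate, repeat rate or power figure for this endpoint, so there is nothing to reproduce for it. The only planning figure used here is 586 per arm. It reproduces from SAP section 5 (19% vs 26%, "Alpha (two sided): 0.05", 80% power): the normal approximation gives 558 per arm, and 558 × 1.05 = 585.9.

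**Direction of the error.** Let X be one participant's number of readmissions, with mean m. The test uses variance m(1 − m) = m − m². The actual variance is E[X²] − m². For whole-number counts X² ≥ X, with equality only when X is 0 or 1. So the test's variance is right if nobody has two readmissions and too small otherwise.

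**Size of the error.** Let VR = Var(X) / [m(1 − m)]. The true size of the nominal 5% test is then about 2 × [1 − Φ(1.96/√VR)].

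**Worked example (assumed).** 85% have none, 12% have one and 3% have two readmissions, so 20% of those readmitted have a repeat.

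- m = 0.12 + 2 × 0.03 = 0.18, although 15% of participants are readmitted.
- E[X²] = 0.12 + 4 × 0.03 = 0.24; Var(X) = 0.24 − 0.0324 = 0.2076.
- m(1 − m) = 0.18 × 0.82 = 0.1476; VR = 0.2076/0.1476 = 1.41.
- True size = 2 × [1 − Φ(1.96/√1.41)] = 9.8%.
- With 586 in the arm, the table would show about 105 readmitted and 481 not (0.18 × 586 = 105.5). The people number about 88 and 498 (0.15 × 586 = 87.9).
- If the other arm had 15% readmitted and no repeats, the plan would compare 18% with 15%, although the share of people readmitted is the same.

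**Range.** Assumptions: 5%, 10%, 15% or 20% of participants readmitted at least once; a constant chance of each further readmission; at most four per person; the same distribution in both arms; 586 per arm; 40,000 simulated trials per scenario; chi-square at 0.05.

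| Chance of a further readmission | VR | True size, counting admissions |
|---|---|---|
| 0% | 1.00 | 0.050 |
| 5% | 1.11-1.13 | 0.061-0.067 |
| 10% | 1.23-1.29 | 0.078-0.087 |
| 20% | 1.52-1.65 | 0.110-0.125 |
| 30% | 1.85-2.11 | 0.149-0.178 |

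The formula and the simulation agree to about 0.003. Counting participants with at least one readmission gives a size of 0.048-0.052 in every scenario.

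**The case against.** The strongest reply is that this is loose drafting and that a per-person outcome is meant. The label says cases, and the chosen test makes sense only for people. Protocol 8.2 writes its specimen endpoint in the same way, with a count of samples standing in for a count of participants. SAP 7.2 says that some derived variables will be described in later versions, so a missing indicator does not prove that events will be tested. This stands as a reading of intent. It does not settle the text, because every stated numerator is a count of admissions and no passage overrides it.

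A second reply is that repeats may be rare. The eight weeks run from enrolment, during the index admission, so the time at risk after discharge is under 56 days. This also stands: at 5% repeats the true size is only 6-7%.

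A third is that little depends on the result. SAP 6.3 reserves inference for the primary objective, Protocol 8.2 powers the trial for the primary endpoint only, and the SAP table shells have no readmission row. That limits the consequence but does not correct the rule.

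A reader might also infer that, because participants who die before discharge stay in the denominator and cannot be readmitted, the plan treats death as success. The documents do not support calling this an error. An all-enrolled denominator fits the intention-to-treat set, and in-hospital, four-week and eight-week mortality are endpoints in their own right, so the competing event is visible. A composite shown alongside would be a useful addition, not a correction.

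**Conclusion.** As written, the endpoint contradicts its own label and can count a participant more than once. If any repeat readmission occurs, the reported proportion is too high and the chi-square/Fisher test is anti-conservative.

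A reader might conclude that the p-value is invalid outright. The documents do not support that: with no repeats, admissions equal readmitted participants and the test is sound. The inflation, from none up to a true size of 15-18% at 30% repeats, depends on a repeat rate that the documents do not give. The direction is certain once repeats occur; the size is not. The figures are for chi-square. Fisher's test tends to run below its nominal level, so its inflation would be somewhat smaller.

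This is a secondary endpoint. The primary analysis and the sample size are unaffected, but the text should be corrected because the rule as stated can give a wrong estimate and a wrong p-value.

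**What to change.** - In Protocol 8.2 (with the synopsis) and SAP 3.4.2.2 and 8.2.3, define the numerator as the number of participants with at least one readmission after initial discharge and within 8 weeks of enrolment.
- Use one definition throughout. SAP 3.4.2.2 restricts the reasons for admission by reference to the exclusion criteria; Protocol 8.2 and SAP 8.2.3 do not.
- Add the yes/no variable to SAP 7.2 and name its CRF source.
- Keep the chi-square/Fisher test for that variable, and report total admissions by arm descriptively. If the number of admissions is itself of interest, analyse it as a rate with a method that allows overdispersion (negative binomial or robust variance).
- Optionally, show death or readmission by week 8 beside it.

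The cost is a wording change in both documents before database lock, with no change to the test, the sample size or the primary analysis. One item needs checking first. SAP 4.4 lists no readmission variable, and Protocol 14.2 gives only the names of the forms, so the documents do not show that readmissions are captured with dates. If they are not, a data item is needed as well.
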